#### **D. Ethical Considerations**

Risks and benefits: The study poses minimal risk to participants. All simulation scenarios will involve fictional, non-identifiable patient cases and will be conducted in a controlled, educational environment. No real patients will be involved at any stage. The main potential risk is discomfort or anxiety during performance assessment; however, participants will be reassured that the study is for research purposes only and not a test of their professional competence, and that their individual results will not be shared with supervisors or used in performance evaluations. Participants may gain educational value from practicing emergency scenarios in a structured environment and becoming familiar with digital decision-support tools. The study may also benefit the hospital by informing the refinement of a context-appropriate tool to strengthen emergency and acute care. At a broader level, the findings will contribute to evidence on the feasibility and effectiveness of digital clinical decision-support systems in rural, resource-limited settings.

Voluntariness, withdrawal, consent: Participation is strictly voluntary. Participants may refuse to take part or withdraw from the study at any time without penalty or consequence to their employment or professional standing. Written informed consent will be obtained prior to enrollment, using a standardized consent form.

Data protection and confidentiality: All data will be de-identified at entry, with no names or personal identifiers collected, and only the University of Milano-Bicocca research team will have access to the raw de-identified data. Hospital management will receive only aggregated results. No identifiable information will be linked to individual performance results. Individual results will not affect employment status, performance evaluation, or professional progression. Data will be stored securely on EU-hosted Kobo Toolbox servers and password-protected Bicocca servers. Data will be retained for 5 years, after which it will be permanently deleted.

Compensation: To minimize disruption of clinical services, simulations will be conducted outside of OPD duty hours. Each participant will receive a modest token of appreciation of 20,000 UGX (corresponding to €5) and a small refreshment upon completion of their sessions. This amount is intended to offset inconvenience and time but does not constitute undue inducement.

Community engagement and dissemination of results: This study is part of a broader collaboration between the University of Milano-Bicocca and [name] Hospital, within a quality improvement program aimed to strengthen emergency services at [name] Hospital. The OASES App is designed to support, rather than replace, frontline clinicians by guiding them through evidence-based triage and management steps and collecting structured data. Stakeholder engagement has been central to the study design and conduction of the study has been approved by the [name] Hospital Medical Director. Hospital leadership and OPD staff were consulted on protocol feasibility, workflow fit, and alignment with ongoing initiatives. A key issue identified during early discussions was staff concern that digital tools might threaten job security. To mitigate this, we will engage staff before enrollment through informational meetings and informal discussions, emphasizing that the App is a supportive tool intended to strengthen, not replace, clinical roles. During and after the study, we will maintain transparency with OPD staff and hospital leadership, providing regular updates and holding dissemination meetings to share findings. Results will be shared with hospital staff, hospital leadership, and published in peer-reviewed journals. Findings will be used to refine the OASES App before clinical deployment.

Ethical and Regulatory Approvals: The study protocol, participant information/consent materials, and data-protection plan have received ethical approval from the Gulu University Research Ethics Committee (GUREC) and the University of Milano-Bicocca Research Ethics Committee, and regulatory clearance from the Uganda National Council for Science and Technology (UNCST). In addition, [name] Hospital (DAMHK) management has approved the conduct of the study on site. All procedures will adhere to the Declaration of Helsinki and applicable Good Clinical Practice principles, as well as the EU GDPR and the Uganda Data Protection and Privacy Act (2019).

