### Exclusion Criteria:

- Individuals who are unable or unwilling to participate in both scheduled simulation sessions.

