## **C.4. Sample Size**

This pilot study will use a feasibility-based sample size, determined by the total number of OPD clinicians available at [name] Hospital. We anticipate enrolling approximately 16 participants, representing all nurses, clinical officers, and nursing assistants currently working in the OPD of [name] Hospital. Each participant will complete 12 simulated scenarios, yielding an estimated 192 scenario-level observations. While not powered to detect small effect sizes, this sample is deemed to be sufficient to assess feasibility, refine study procedures, and provide preliminary effect estimates to inform the design and power calculations of a subsequent larger trial.

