## **C.6. Randomization and allocation**

Participants will be randomized to the order of study conditions—App-assisted (intervention) vs. standard practice (control)—using computer-generated permuted blocks of size 2, stratified by cadre (nurse/nursing assistant vs clinical officer) to ensure balance across professional groups. The randomization list will be computer-generated in advance by a member of the research team not involved in recruitment or outcome assessment and stored in a password-protected master sheet. Participant IDs will be assigned sequentially after written consent in order of recruitment; each ID is then linked to a pre-specified condition sequence from the master sheet.

To control for case content and ordering effects, matched scenario pairs were created for each condition (A-set for one period, B-set for the other period), with random assignment of A vs. B to the first or second period per participant. Within each period, the case order (1–6) was independently randomized. Thus, for every participant the master sheet specifies: (i) intervention sequence, (ii) period assignment of A vs. B cases, and (iii) the randomized within-period case order.

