### C.8. Simulation and Scenarios

Each participant will complete 12 facilitated clinical vignette scenarios, with six scenarios per study arm (two diarrhea, two dyspnea, and two seizures). Scenarios will be adapted from WHO training materials for emergency care (e.g., *Basic Emergency Care* course, *Emergency Triage Assessment and Treatment* guidelines) and tailored to reflect common emergency presentations in the OPD of [name] Hospital. Both adult and pediatric cases will be included, varying in severity and presentation to capture the spectrum of conditions typically encountered. Draft cases will undergo expert review and pilot testing with representative clinicians to ensure clarity, realism, and contextual relevance. Cases will be designed in matched pairs to ensure comparable content and difficulty between study periods, with equivalence determined by expert review and pilot testing. Scenarios will be balanced for complexity, number of critical actions, and expected completion time.

Cases will be delivered verbally by a trained facilitator, who will respond only to participant questions to simulate real-world information gathering. Facilitators will log which key history and examination items are elicited using a structured tick-box script.

At two predefined points in each vignette, participants will record their diagnostic and treatment plan:

1. Initial assessment stage – working impression, immediate treatments, and diagnostic tests ordered.
2. Post-investigation stage – final diagnosis, disposition decision, treatment plan and follow-up plan.

Each participant's simulation session will last approximately one hour. All sessions will be scheduled during off-duty hours to ensure voluntary participation and to avoid disruption of patient care.

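### Both case sets are in use in both periods among co-workers, the participant script does not ask them to keep cases private, and staff updates have no content limit, so the crossover estimate is open to peer leakage

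*Combined protocol and SAP*

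**What the plan says.** Section C.6 creates two matched case sets, "with random assignment of A vs. B to the first or second period per participant". Some participants therefore meet set A first and others set B first, and both sets are live in both periods. Section C.8 adds: "Cases will be designed in matched pairs to ensure comparable content and difficulty between study periods".

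Section C.4 describes the sample: "We anticipate enrolling approximately 16 participants, representing all nurses, clinical officers, and nursing assistants currently working in the OPD". Section C.1 fits the study into two weeks with at least seven days between a participant's two sessions. Section C.7 sends participants back to ordinary duties in that interval and withholds only the App.

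The participant instructions in Appendix C tell participants that their own responses are confidential. They do not ask them to avoid talking about the cases. Section D, on community engagement, says "During and after the study, we will maintain transparency with OPD staff and hospital leadership, providing regular updates"; the same sentence goes on to meetings at which findings are presented. It does not say what an update given before the last session may contain.

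On piloting, section C.8 says "Draft cases will undergo expert review and pilot testing with representative clinicians" without naming where those clinicians come from. The only exclusion in section C.3 is: "Individuals who are unable or unwilling to participate in both scheduled simulation sessions".

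**The concern.** The washout, the two case sets and the random case order stop a participant from meeting the same case twice and limit the effect of that participant's own memory. None of them deals with what one colleague tells another. Several scored answers are short enough to pass on in a sentence: a triage colour, admit or discharge, or, for sample case A001, that no tests are needed.

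If leaked content raised both arms equally in period 2, the period term would take up nearly all of it. The difficulty arises if control gains more than App. That is plausible, because in App sessions the guidance is already on the screen. The result would be an arm-by-period difference, which the additive arm and period terms in section C.11 do not remove from the arm effect.

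Two things are at stake. The crossover analysis of the primary outcome is the only analysis that section C.11 calls confirmatory. And section C.4 intends the estimate to inform the power calculation of the next trial.

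**Working it through.** **The plan's own figure.** "Each participant will complete 12 simulated scenarios, yielding an estimated 192 scenario-level observations": 16 × 12 = 192, which reproduces. There is no power calculation to reproduce, because the sample size is feasibility-based.

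**Exposure.** Inputs: 16 participants (C.4), hence 15 co-workers each; 50:50 assignment to A first or B first, taken as independent between participants (C.6).

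- Expected co-workers who met a participant's period-2 set in period 1: 15 × 0.5 = 7.5. With an exact 8:8 split it is 8 of 15.
- Probability of at least one: 1 − 0.5^15 = 0.99997.
- Of these, about half used the App in period 1: 7.5 × 0.5 = 3.75, or roughly 4 of 15 who saw App advice on those cases.

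**Bias on the proportion scale.** In the two-period crossover the arm estimate is

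½ [(App in period 1 − control in period 2) + (App in period 2 − control in period 1)].

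Let leakage add Lc to control and La to App in period 2, and let the true difference be d. The estimate is then d − (Lc − La)/2. The documents give no control level, effect or leakage. I assume control 0.50 and d = 0.20, and show a range for the leakage:

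| Lc | La | Estimate |
|---|---|---|
| 0.10 | 0.10 | 0.20 − 0 = 0.200 |
| 0.10 | 0.05 | 0.20 − 0.025 = 0.175 |
| 0.10 | 0 | 0.20 − 0.05 = 0.150 |
| 0.20 | 0 | 0.20 − 0.10 = 0.100 |
| 0.05 | 0.10 | 0.20 + 0.025 = 0.225 |

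**Check on the logit scale.** The planned model is binomial with a logit link, so the formula was checked by simulation: 16 participants, 6 cases per period, 300 replicates. Assumed values were 6 items per case, participant SD 0.5 and App effect 0.8 on the logit scale. A binomial GLM with arm, period and sequence stood in for the mixed model.

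| Period-2 leak, logit scale (control, App) | Crossover estimate | First-period estimate |
|---|---|---|
| 0, 0 | 0.180 | 0.180 |
| 0.4, 0.4 | 0.177 | 0.178 |
| 0.4, 0 | 0.135 | 0.183 |
| 0.8, 0.8 | 0.161 | 0.177 |
| 0.8, 0.4 | 0.126 | 0.188 |
| 0.8, 0 | 0.083 | 0.182 |

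Equal leakage largely cancels, with some compression near the ceiling when it is large. Unequal leakage does not cancel. The first-period estimate is unaffected by period-2 leakage, but without leakage its spread across replicates is 0.065 against 0.028 for the crossover.

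**Leakage within period 1.** Section C.8 gives about one hour per session. If one pair of facilitators runs the sessions one at a time, period 1 takes 16 × 1 = 16 hours of off-duty time. That would probably fall on several days, though the schedule is not stated. Later first sessions could then be affected too.

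**Consequence for the next trial.** Required size varies with 1/effect². Other things equal, planning on 0.15 instead of 0.20 multiplies it by (0.20/0.15)² = 1.78; planning on 0.175 multiplies it by (0.20/0.175)² = 1.31.

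**The case against.** The strongest reply is that the plan already has defences and that little of use can leak. Section C.11 includes a first-period-only analysis to be compared with the crossover result, and exploring learning and carryover is a stated secondary objective. Differential leakage would also show in the sequence term, as (Lc − La)/2. Only about 4 of 15 colleagues would have seen App advice on the relevant cases. Facilitators release only what is asked for, no teaching is given, and Appendix E requires correct dose and reassessment for treatment items, which hearsay carries poorly.

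Much of this stands as a limit on the size. It does not remove the gap. The first-period analysis is not confirmatory, is less precise, and does not cover talk within period 1. The sequence term flags the bias without correcting it, and with 16 participants it has little power to do so. Case facts alone can still help with triage, tests and diagnosis.

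A reader might also infer more than the documents support:

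- That leakage will occur and will shrink the effect. Nothing shows that it occurs, and the direction depends on which arm gains more.
- That section D promises to disclose cases. The passage is about engagement and follows staff worries over job security. It simply leaves the content of updates open.
- That participants piloted the cases. The source of the pilot clinicians is not stated, so this is only possible. Such exposure would affect both periods, not only the second.
- That no confidentiality request exists anywhere. The consent form and Appendix A are not in the text available, so a request there cannot be ruled out. The point concerns the script.

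**Conclusion.** The structural gap is real. Nearly every participant will have colleagues who have already met their period-2 cases, and no safeguard in the available text addresses talk between them. The resulting bias is conditional: −(Lc − La)/2 on the proportion scale, towards no effect if control gains more, about nil if the gains are equal, and away from no effect if App gains more. With an assumed effect of 0.20 and a control gain of 0.10, the estimate lies between 0.15 and 0.20 for App gains from 0 to 0.10. These sizes rest on assumed leakage and are not a forecast. No single percentage of shrinkage can be derived from the documents. The change is worth making because it is cheap, it protects the confirmatory estimate, and it cannot be supplied once first sessions have been held.

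**What to change.** 1. In the participant instructions of Appendix C, and again at the end of session 1, add: *Please do not discuss the cases or the App's advice with colleagues until all sessions are finished.*
2. In section D, state that updates to outpatient staff before the last session contain no case content, App advice or interim findings.
3. In section C.8, where piloting is still to be done, draw the pilot clinicians from outside the participant pool. If a participant has already seen the cases, record it and repeat the analysis without that person as a sensitivity analysis. Excluding such people outright would reduce a sample that is meant to take in every eligible clinician, so that is not recommended.

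The number of participants, the 192 observations, the schedule and the primary model stay as they are. The cost is a few sentences of wording and a delay of at most two weeks in sharing findings with staff. Pilot clinicians from outside the department may also resemble its staff somewhat less closely.

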## Appendix B. Baseline Survey

### Participant information

This survey collects background information to help us understand participants' experience and context. Your answers are confidential and will only be used for research purpose. Please select the response that best applies to you.

Participant ID: (assigned after randomization)

1. Cadre:

- ☐ Clinical Officer
- ☐ Nurse
- ☐ Nursing Assistant

2. Highest professional qualification:

- ☐ Bachelor's Degree
- ☐ Diploma
- ☐ Ordinary Certificate or Uganda Advanced Certificate of Education (UACE)
- ☐ Uganda Certificate of Education (UCE)
- ☐ Primary School Leaving Certificate

3. Years of clinical experience: (numeric entry)

4. Years worked in Kalongo OPD: (numeric entry)

5. Trainings completed in past 24 months: (select all that apply)

- ☐ None
- ☐ Emergency Triage, Assessment and Treatment (ETAT)
- ☐ Basic Life Support (BLS)
- ☐ Advanced Cardiac Life Support (ACLS)
- ☐ Advanced Trauma Life Support (ATLS)
- ☐ Basic Emergency Care (BEC)
- ☐ Integrated Management of Childhood Illness (IMCI)
- ☐ Other (specify)

6. How often do you use national or WHO guidelines in your OPD work?

- ☐ Never
- ☐ Rarely
- ☐ Sometimes
- ☐ Often
- ☐ Always

7. How often do you personally manage patients with the following conditions in the OPD?

- Severe diarrhea
  - Dyspnea
  - Seizures
- Response options for each condition:
- ☐ Never
  - ☐ Rarely (less than once per month)
  - ☐ Occasionally (about once per month)
  - ☐ Regularly (about once per week)
  - ☐ Frequently (several times per week)

8. Do you have regular access to an Android smartphone or tablet?

- ☐ Yes
- ☐ No

9. How comfortable are you using mobile apps on a smartphone or tablet?

- ☐ Not at all comfortable
- ☐ Slightly comfortable
- ☐ Somewhat comfortable
- ☐ Moderately comfortable
- ☐ Extremely comfortable

10. Have you ever used a mobile App for clinical decision support?

- ☐ Never
- ☐ Rarely
- ☐ Sometimes
- ☐ Often
- ☐ Always

11. If yes, which ones? List the names here. (free text entry)

11. Have you ever participated in a simulation-based clinical training?

- ☐ Never
- ☐ Rarely
- ☐ Sometimes
- ☐ Often
- ☐ Always

## Appendix C. Case Script and Facilitator Tick-Box Checklist (Sample: Diarrhea – Pediatric)

### Facilitator instructions:

- Provide information only when the participant asks.
- Do not volunteer information unless explicitly prompted.
- Tick each item when it is asked about.
- Critical WHO-required actions are underscored.

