### C.7. Intervention and Control

Experimental arm (OASES App): Participants will use the OASES tablet-based CDSS, which incorporates the Interagency Integrated Triage Tool (IITT) and three condition-specific algorithms (diarrhea, dyspnea, and seizures) derived from WHO and Uganda Clinical Guidelines. No formal training sessions will be conducted; however, participants will receive a brief orientation walk-through of the App immediately prior to its use.

Control arm (standard practice): Participants will manage simulated cases without the App, relying on their usual knowledge and clinical experience. Standard resources available in OPD, including paper-based versions of the IITT and Uganda Clinical Guidelines, will be available for reference.

All participants will complete both arms using a crossover design, with a washout period of at least one week between conditions. During the washout, participants will return to their normal OPD duties without access to the OASES App. No additional clinical teaching or training will be provided during the study period.

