### C.9. Outcomes

Primary outcome:

- Guideline-adherent management: Proportion of pre-specified, guideline-consistent critical management actions (diagnostics and treatments) completed per vignette (proportion 0-1). Participant responses recorded at the initial assessment and post-investigation stages will be scored against a gold-standard answer key derived from WHO guidelines (Basic Emergency Care assessment checklists, ETAT performance checklists, Integrated Management of Childhood Illness checklists). Scoring will be performed by two independent assessors, blinded to allocations, mapping free text to binary items (performed correctly vs. not performed/incorrect). Disagreements will be resolved by consensus.

Secondary Outcomes:

- Triage accuracy: Correct assignment to Interagency Integrated Triage Tool (IITT) category (Red/Emergency, Yellow/Urgent, Green/Non-urgent) compared with the case-specific expected category (binary). Scoring will be performed by two independent assessors, blinded to allocations.
- Disposition appropriateness: Appropriateness of the disposition decision (hospitalize, discharge) compared with case-specific expected disposition in the answer key, based on

WHO/Uganda guidelines (binary). Scoring will be performed by two independent assessors, blinded to allocations.

- Diagnostic accuracy: Correctness of working impression (initial stage) and final diagnosis (post-investigation stage), compared with case-specific diagnostic labels in the answer key, based on WHO/Uganda guidelines (binary). Scoring will be performed by two independent assessors, blinded to allocations, mapping free text to binary items (performed correctly vs. not performed/incorrect).
- Guideline-adherent evaluation (process quality): Proportion of critical history and examination items elicited by the participant during the vignette, compared with case-specific list of critical items derived from WHO guidelines (proportion 0-1). Scoring will be performed by two facilitators during each simulation session using the facilitator tick-box logs.
- Time to completion: Duration needed to complete each vignette, measured by facilitators (continuous).
- Usability: Total score on System Usability Scale (SUS), a widely validated 10-item tool for evaluating software systems in healthcare and other fields (continuous).

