### C.10. Data Collection and Management

Data will be collected electronically using Kobo Toolbox, an open-source, web-based platform developed by the Harvard Humanitarian Initiative for data collection in resource-limited and field settings (<https://www.kobotoolbox.org/>).

- Baseline data: Prior to randomization, participants will complete a baseline survey capturing demographic and professional characteristics, prior emergency training, and digital literacy (**Appendix B**).
- Simulation data: During each vignette, two facilitators (emergency medicine clinicians from the study team) will deliver cases, log process measures using structured tick-box forms (**Appendix C**), and capture start/end times. Any discrepancies will be reconciled immediately after the session. Participants will record clinical decisions directly into Kobo Toolbox forms at predefined stages (**Appendix D**).
- Outcome scoring: Responses will be exported in de-identified forms and scored by two independent assessors, blinded to allocation, using pre-defined gold-standard answer keys (**Appendix E**). The two assessors will be two clinicians not involved in App or case development. Discrepancies will first be discussed by the two reviewers to reach consensus; if disagreement persists, a third senior adjudicator (not involved in App or case development) will provide the final decision.
- Post-simulation survey and interview: After completing sessions that involve App use, participants will complete a structured electronic questionnaire assessing usability (SUS), perceived usefulness, trust, satisfaction, and feasibility (**Appendix F**). To complement these quantitative measures, the two facilitators will also conduct brief semi-structured interviews with each participant immediately after their simulation session (**Appendix G**). Interviews will not be audio-recorded; instead, facilitators will take contemporaneous field notes, which will be expanded into detailed summaries for subsequent qualitative analysis.

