**Facilitator Summary (to be entered in Kobo Toolbox at the end of the simulation session):**

- Participant ID: (assigned after randomization)
- Case ID:
- Case start time:
- Case end time:
- Guideline-adherent evaluation score (n° of ticked underscored items): \_\_\_\_/8
- Notes/comments:

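### The process-quality tick sheet shows unblinded facilitators which items count, an avoidable cue on a secondary, exploratory outcome

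*Combined protocol and SAP*

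**What the plan says.** Section C.9 has management, triage, disposition and diagnosis scored by two independent assessors blinded to allocation. Process quality is handled differently: "Scoring will be performed by two facilitators during each simulation session using the facilitator tick-box logs". Section C.10 says who these raters are: "During each vignette, two facilitators (emergency medicine clinicians from the study team) will deliver cases, log process measures using structured tick-box forms". No blinding is stated for them, and C.10's condition that assessors had no part in developing the App or the cases is not extended to them. In the App arm, section C.7 states: "Participants will use the OASES tablet-based CDSS". This happens in front of the facilitators.

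The sheet is shown in Appendix C. The ticking rule is "Tick each item when it is asked about", and the next line adds that "Critical WHO-required actions are underscored". The Facilitator Summary, entered in Kobo Toolbox at the end of the session, asks for one process figure, the number "of ticked underscored items", out of 8 in the sample case.

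The safeguards are a structured script, facilitators who answer only what is asked (C.8, Appendix C), two loggers with discrepancies reconciled straight after the session (C.10), and Cohen's kappa per item with an ICC for totals (C.11). C.11 treats all secondary outcomes as exploratory.

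**The concern.** Whether an item was asked about is sometimes a judgement. Composite lines such as hydration status or danger signs can be half-asked, and the plan has no rule for vague, partial or App-prompted questions. A rater who knows both the arm and the scored boxes can resolve doubtful ticks, without intending to, in a way that moves the score. If that happens more in one arm, it goes straight into the App-control difference.

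Process quality is a named secondary objective, and section C.4 intends the pilot's effect estimates to inform a larger trial. An avoidable bias could be carried into that design.

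**Working it through.** **Plan's own figure.** C.4 gives 16 participants × 12 scenarios = 192 observations, which reproduces. With six scenarios per arm (C.8), that is 16 × 6 = 96 per arm. The sample size is feasibility-based, with no SD or effect size, so everything below that needs one is an assumption.

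**Who knows what.** The raters of the four response-based outcomes work from de-identified exports and are blinded. The raters of process quality know the arm (an inference, but the set-up allows no other reading) and know the scored items (stated). Only the second can be removed.

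**Weight of one tick in case A001.** The denominator is 8, so one tick is 1/8 = 12.5 points. The sheet prints 5 present-illness boxes + 9 past and social history boxes + 10 examination boxes (counting the vital-signs line and its four sub-items) = 24. So 8/24, or one third, are scored, if all eight lie among these boxes.

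**Illustrative bias.** Let q be the average number of extra credited doubtful ticks per App vignette relative to control (assumed). If all land on scored items, bias = q/8. If they fell evenly over all 24 boxes, bias = q/24.

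| q | q/8 (points) | q/24 (points) |
|---|---|---|
| 0.10 | 1.25 | 0.4 |
| 0.25 | 3.1 | 1.0 |
| 0.50 | 6.25 | 2.1 |

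The ratio of 3 is the most that hiding the marks could achieve under this reasoning. It is not an expected gain.

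**Scale against sampling error.** A simple approximation on the raw proportion scale is SE = SD × √(2/96). For an assumed vignette SD of 0.15 to 0.25, this gives 2.2 to 3.6 points. At q = 0.25 the bias of 3.1 points is about one SE. With no true effect, the chance of nominal two-sided p < 0.05 is 1 − Φ(1.96 − bias/SE) + Φ(−1.96 − bias/SE). It rises from 5% to about 30% (SD 0.15), 19% (SD 0.20) or 14% (SD 0.25).

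**Would kappa reveal a shared leaning?** Assume a true elicitation rate of 0.6 and a 5% independent error per rater. Agreement is 0.95² + 0.05² = 0.905.

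- No leaning: the observed tick rate is 0.6 × 0.95 + 0.4 × 0.05 = 0.59. Chance agreement is 0.59² + 0.41² = 0.516, so kappa = (0.905 − 0.516)/(1 − 0.516) = 0.80.
- Both raters wrongly credit the same 20% of unasked items: the credited rate is 0.6 + 0.4 × 0.2 = 0.68, and the observed rate is 0.68 × 0.95 + 0.32 × 0.05 = 0.66. Chance agreement is 0.552, so kappa = (0.905 − 0.552)/(1 − 0.552) = 0.79.

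The score rises by about 7 points while kappa hardly moves.

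**The case against.** The strongest reply is that the main weakness, live rating by people who see the arm, cannot be removed, and the marks may add little to it. Doubt arises about a particular half-asked item and does not scatter over 24 boxes. If that item is scored, a lenient tick costs 1/8 whether or not the line is underscored. The raters are emergency clinicians who may recognise critical items unmarked. A reader might infer from the table that an unmarked sheet removes two thirds of the bias. The documents do not support that: threefold is an upper limit, and the true gain could be near zero. This part of the reply stands.

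A reader might also infer that adding up the score in the session is itself a source of bias. It is not: once the ticks exist, the total is arithmetic, and code would return the same number apart from counting slips. Nor do the documents say that item ticks are discarded; the summary simply lists only a total.

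The existing safeguards count for something. Answering only what is asked limits any prompting, and two loggers with reconciliation limit one rater's idiosyncrasy. They do not address a shared leaning, as the kappa calculation shows. Finally, marked items are easier to log while delivering a case. That is a fair cost, but a modest one, because facilitators must already tick every item asked about.

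**Conclusion.** The point holds as an avoidable cue given to unblinded raters, and it is worth correcting before the sessions start. It is not evidence that the App effect on process quality is biased: the plan gives no basis for the direction or size. The value of q, the SD and the error rates are assumptions. The 8-of-24 layout comes from one sample case, and the underscores are not visible in the text available, so it cannot be said which items are scored. What is firm is that one tick is worth 12.5 points in case A001, and that agreement between two raters with the same knowledge would not expose a common leaning.

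The reach is limited to a secondary, exploratory outcome in a feasibility-sized pilot. A reader might extend the concern to the primary outcome, but its scoring rests on participants' recorded responses and blinded assessors, so the tick sheet does not enter it.

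**What to change.** - Use a tick sheet without underscoring in the room, and drop the line saying that critical items are marked.
- Record each facilitator's item-level ticks in Kobo before reconciliation, and keep them alongside the reconciled version. The per-item kappa in C.11 needs these data anyway.
- Hold the pre-specified, case-specific critical-item list with the answer keys and apply it in the analysis code, in place of the facilitator's count out of 8.
- State in C.9 and in the report that process quality is rated by facilitators who know the arm, as a limitation that the unmarked sheet reduces but does not remove.

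The cost is reprinting the scripts, a short scoring step in code, and entering item ticks rather than one total. Critical items will stand out less during logging, so a scored tick could be missed; the second logger limits that.
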